The primary aim of the study is to determine whether the MyREADY Transition™ BBD App intervention will result in improved self-management and self-advocacy skills (major components of transition readiness), compared to usual care for youth with BBD between 15 and 17 years of age. The MyREADY Transition™ BBD App intervention has the potential to improve perception of quality of care and youth and parent/caregiver experiences during the transition process; and a potential also for cost efficiencies across pediatric and adult provincial health care systems. Analysis for the primary aim of the study will be led by [name] at McMaster University.

Hypothesis: Youth who use the MyREADY Transition™ BBD App intervention will have higher self-management change scores (a major component of transition readiness), over a 6-month period compared with youth receiving usual care. Self-management change scores will be measured using the Transition Readiness Assessment Questionnaire (TRAQ).⁹

Secondary aims of the study include exploring the contextual experiences of youth using the MyREADY Transition™ BBD App (e.g., their satisfaction with the App and its content, *how* it is being used and

NOTE: CTO#1666 Amendment approved by HiREB on January 9, 2023. Target sample was 264 participants; however, we randomized 52 participants, and did not complete the full-scale RCT. Linking health card numbers with provincial administrative data is labour intensive and costly, and the small number would not provide meaningful results. As approved by ethics, we dropped the health economic outcome analysis (Health card number linking, Health Utilities Index (HUI), Resource Use Questionnaire (RUQ)) and destroy stored health card number data.

integrated during transition, and perceived value); as well as the interactive processes of youth, their parents/caregivers and health care providers around use of the intervention (e.g., that support/hinder use). Analysis for the secondary aim of the study will be led by [name] at McGill University.

In addition, both [name] and [name] will work with the Health Economics team within the CHILD-BRIGHT network who will support the data collection and analysis for the health economics outcomes, with a few key objectives across all projects:

- To compare the patterns of health service use for the intervention compared to current standard of care.

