number of participants in each of two groups: intervention group (132) and control group (usual care) (132). Since participants will be recruited from only four regions, we will model the effect of region as a fixed effect rather than a random effect.¹⁸ This will allow region-specific intervention effects to be modelled (i.e. region by intervention interaction effects). If no region by intervention interactions are found, the interaction terms will be dropped from the model and we will estimate an overall intervention effect. Since the region by intervention interaction is unknown, we take a conservative approach with a sample size calculation that will enable detection of an intervention effect within each site. This will allow for a properly powered analysis of the site by treatment interaction. The primary outcome measure (Transition Readiness Assessment Questionnaire, TRAQ)⁹ has been validated on a sample of youth with congenital heart disease and in the absence of literature specific to BBD, we will base our sample size calculations on these findings. We anticipate a mean TRAQ self-management baseline score of 3.01 (SD 1.02) (out of a possible 5.0) as reported for youth (with congenital heart disease) without a transition intervention and an anticipated mean score of 4.0 at 6 months post-intervention resulting in a change score of 1 (i.e., 1 SD), with $\alpha=0.05$ and 90% power.¹⁹ Therefore, in each region, we will require 23 youth in each of the 2 arms (total of 46) x 4 regions = 184. Estimating 30% attrition, we will enroll 264 participants.

Inclusion Criteria

- Youth with chronological age between 15 and 17 years of age (i.e. before 18th birthday), in one of the four study regions, followed in pediatric care and for whom a discharge from pediatric care is planned but not for at least 6 months.
- A diagnosis of one of the following neurological BBD: autism spectrum disorder, cerebral palsy, epilepsy, spina bifida, or fetal alcohol spectrum disorder.
- Cognitive ability to provide informed consent and the ability to read and understand English or French
- Access to internet and a smartphone, iPad/tablet or desktop computer.
- TRANSITION-Q²⁰ score >40 (as a screen to define a minimum threshold for transition readiness based on our earlier work).

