Participants allocated to the usual care group will not know the details of the electronic intervention being offered to the intervention group. Due to the nature of the intervention, participants cannot be blinded to group allocation, however outcome assessment and data analysis will be blinded. Our RCT protocol is registered with ClinicalTrials.gov (NCT03852550).

In order to track participants according to the CONSORT guidelines²³⁻²⁴, a de-identified recruitment log of potential candidates at all participating sites will be kept, recording inclusion/exclusion criteria and reasons for eligible youth patients not being recruited or randomized.

Intervention and Control Conditions

Participants randomized into the control group will receive their clinic's standard of care. Any support the youth (and parents/caregivers) receive as part of any ongoing transition programs in usual care will be documented by youth, parents/caregivers and health care providers. Documentation will include an inventory checklist with a section to add any specific information or individualized approach relevant to the transition process. We will also ask participants and their parents/caregivers what they perceive as supports and if they were received.

NOTE: CTO#1666 Amendment approved by HiREB on January 9, 2023. Target sample was 264 participants; however, we randomized 52 participants, and did not complete the full-scale RCT. Linking health card numbers with provincial administrative data is labour intensive and costly, and the small number would not provide meaningful results. As approved by ethics, we dropped the health economic outcome analysis (Health card number linking, Health Utilities Index (HUI), Resource Use Questionnaire (RUQ)) and destroy stored health card number data.

Participants randomized into the intervention group will be provided the link to download the MyREADY Transition™ BBD App. The RA will be trained to facilitate the App download and registration. The RA will demonstrate the App, ensuring that the participant understands how to access all the features. The MyREADY Transition™ BBD App intervention is fully described in Appendix B. The App will be translated into French, and the translation will be done by professional translators of the firm Essentiel Plus.

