Primary: To determine whether the MyREADY Transition™ BBD App intervention will result in improved transition readiness	Primary: 
 Change in TRAQ self-management score from Baseline to 6 months. 	Intervention > Control	T-Test; p<0.05
	Secondary: 
 Change in TRAQ self-advocacy score from Baseline to 6 months. 	Intervention > Control	T-Test; p<0.05
	Secondary 
 Health care transition experience 	Individual semi-structured interviews	Qualitative Methods
Secondary: What is the effect of the MyREADY Transition™ BBD App intervention for	Primary: Population Health 
 Serious illness (hospitalizations, ICU admission questions from Resource Use Questionnaire 	Intervention > Control	T-Test for continuous outcomes Chi-square test

NOTE: CTO#1666 Amendment approved by HiREB on January 9, 2023. Target sample was 264 participants; however, we randomized 52 participants, and did not complete the full-scale RCT. Linking health card numbers with provincial administrative data is labour intensive and costly, and the small number would not provide meaningful results. As approved by ethics, we dropped the health economic outcome analysis (Health card number linking, Health Utilities Index (HUI), Resource Use Questionnaire (RUQ)) and destroy stored health card number data.

improving health and use of health systems?	
 • PedsQL™ Pediatric Quality of Life • Patient Activation Measure (PAM) (health-related self-efficacy) • TRANSITION-Q 		for hospitalization
	Secondary: 
 • Utilization MyREADY Transition™ BBD App 	User metrics built into MyREADY Transition™ BBD App intervention to assess the extent to which various components of the intervention are accessed	Descriptive
	Secondary: Cost utility/cost-effectiveness 
 • Health Utilities Index® (Hui2/3) • Resource Use Questionnaire 	Evaluate changes in patients' health in relation to changes in cost to assess if the intervention represents an efficient allocation of health care resources	Descriptive; Cost-effectiveness analysis with support from Child-Bright health economics network team

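### Is the 90% power per region undermined because the sample size uses a before-after rise and a baseline SD in place of a between-arm difference in change and its SD?

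*Combined protocol and SAP*

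**What the plan says.** The primary hypothesis (STUDY AIMS AND HYPOTHESIS) is that App users "will have higher self-management change scores (a major component of transition readiness), over a 6-month period compared with youth receiving usual care". Table 1 (STATISTICAL ANALYSIS) gives the primary outcome as "Change in TRAQ self-management score from Baseline to 6 months", tested by a t-test of intervention against control at p<0.05.

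The SAMPLE section takes its inputs from a trial in another population: "We anticipate a mean TRAQ self-management baseline score of 3.01 (SD 1.02"), "as reported for youth (with congenital heart disease) without a transition intervention". It then adds "an anticipated mean score of 4.0 at 6 months post-intervention resulting in a change score of 1 (i.e., 1 SD"), "with $\alpha=0.05$ and 90% power". From this it obtains 23 youth per arm in each of four regions, 184 in all, and 264 after 30% attrition. It explains the regional sizing by the unknown region by intervention interaction: "we take a conservative approach with a sample size calculation that will enable detection of an intervention effect within each site".

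Neither SAMPLE nor STATISTICAL ANALYSIS gives an expected change under usual care, an SD of the 6-month change, or a baseline to 6-month correlation.

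**The concern.** A t-test on change scores needs two planning inputs: the difference between arms in mean change, and the SD of change. The SAMPLE section appears to supply neither. Its effect is the rise expected in treated youth, 4.0 − 3.01 = 0.99, and its SD belongs to a score taken at one time point.

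The rise equals the between-arm difference only if usual-care youth do not change. The documents give some reason to doubt that. Under Intervention and Control Conditions, "Any support the youth (and parents/caregivers) receive as part of any ongoing transition programs in usual care will be documented", so control youth may receive transition programs. Under Inclusion Criteria, the mean TRANSITION-Q score in a validation sample is 53 at age 15 and 59 at age 17. That is another scale and a comparison of age groups, so it yields no TRAQ figure, but it suggests that readiness may rise without the App.

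The baseline SD equals the SD of change only if the correlation between the two visits is 0.5, taking equal SDs at both visits. If either condition fails, the power in each region is not the stated 90%, and that figure sets the total of 184 and 264.

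**Working it through.** **Inputs from the documents.** Baseline mean 3.01 and SD 1.02; expected mean 4.0 at 6 months; alpha 0.05; power 90%; 1:1 allocation; four regions; 30% attrition. The number of sides is not stated; only a two-sided test reproduces 23 per arm (one-sided versions need 18 or 19).

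**Reproducing the plan's figures.** For two means, n per arm = 2(z₀.₉₇₅ + z₀.₉₀)² / (d/SD)², with z values 1.960 and 1.282. Power at 23 per arm is by the noncentral t distribution with 44 degrees of freedom.

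| Difference / SD | n, normal formula | n, exact t | Power at 23 per arm |
|---|---|---|---|
| 1 / 1 | 21.0 → 22 | 23 | 91.2% |
| 1 / 1.02 | 21.9 → 22 | 23 | 90.2% |
| 0.99 / 1.02 | 22.3 → 23 | 24 | 89.6% |

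So 23 per arm follows from the printed effect of 1 point (1 SD) by exact t, or from 0.99/1.02 by the normal formula. A one-sample before-after test of 1/1.02 would need 14, so the plan did compute a two-arm comparison. Then 23 × 2 × 4 = 184. For attrition, 23/0.7 = 32.9, rounded up to 33, and 33 × 8 = 264.

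**Varying the usual-care change** (assumed values; SD of change 1.02; difference = 0.99 − gain):

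| Usual-care gain | Power per region, 23 per arm | Power pooled, 92 per arm |
|---|---|---|
| 0 | 89.6% | >99.9% |
| 0.1 | 82.5% | >99.9% |
| 0.2 | 72.9% | 99.9% |
| 0.3 | 61.2% | 99.5% |
| 0.5 | 35.7% | 90.0% |

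The starting value matters little. At a gain of 0.1, power is 83.3% when starting from 1/1.02 and 84.7% when starting from 1 SD.

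**Varying the correlation** (assumed values; equal SDs at both visits; SD of change = 1.02 × √(2(1 − ρ))):

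| ρ | SD of change | Power per region, no usual-care gain | Power pooled, usual-care gain 0.5 |
|---|---|---|---|
| 0.3 | 1.21 | 77.7% | 78.2% |
| 0.4 | 1.12 | 83.6% | 84.1% |
| 0.5 | 1.02 | 89.6% | 90.0% |
| 0.6 | 0.91 | 94.9% | 95.2% |
| 0.7 | 0.79 | 98.6% | 98.7% |

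The two assumptions can offset each other. At ρ = 0.7 and a usual-care gain of 0.2, power per region is 91.2%.

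**Detectable differences at 90% power.** These are 0.98 SD of change at 23 per arm and 0.48 SD at 92 per arm. The first is the 1 SD that the SAMPLE section prints.

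**The case for a change.** The strongest case for a change is that the SAMPLE section makes its claim region by region, and that claim is sensitive to an assumption it does not state. Any improvement under usual care lowers power, and a gain of 0.1 points already costs about 7 percentage points (89.6% to 82.5%). Reading 3.01 as the untreated mean at 6 months does not remove the assumption, because usual care must still stay at 3.01. Rewording would cost one paragraph, and readers may judge the result in 52 participants against the planned power.

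The omission and its direction for usual-care change both stand. The rest is weaker:

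- The SD has no established direction. Above a correlation of 0.5 the value 1.02 is cautious, below it optimistic, and the documents do not say which applies.
- The word conservative in that section describes sizing each region separately because the interaction is unknown. It makes no claim about the mean or the SD. In that sense it is borne out, since the pooled test has ample reserve.
- The reader is told the size of the effect: 1 point, 1 SD. An experienced analyst will take this as the standardised difference between arms, and it is what 23 per arm delivers.
- Having no slack at the assumed inputs is true of any sample size solved for a target power.
- The inputs are cited to a published trial that cannot be consulted here. One can say that they are not justified in this text, but not that they lack justification.

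**Conclusion.** No change follows. The plan leaves two assumptions unwritten: no change under usual care, and an SD of change of about 1.02. Nothing in the documents shows that the stated power is wrong. All three sample-size figures reproduce for a two-arm difference of about 1 SD, and the stated 90% corresponds to 89.6% to 91.2% depending on rounding.

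The sensitivity is confined to the regional claim: 82.5% to 61.2% for assumed usual-care gains of 0.1 to 0.3, and 77.7% to 98.6% for assumed correlations of 0.3 to 0.7. The t-test in Table 1 has no region term, and the SAMPLE section plans an overall effect if no interaction is found. That pooled comparison keeps 90.0% power at a usual-care gain of 0.5 with an SD of change of 1.02; at a correlation of 0.3 the same gain would leave 78.2%. All these ranges are assumptions, because the documents supply neither input.

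Writing the assumptions down would be tidy, but it would change no sample size, test or conclusion. The amendment note repeated through the protocol says that 52 of the planned 264 were randomised and the full-scale trial was not completed. The planned regional power can therefore no longer be attained under the plan's inputs, and rewriting that calculation after recruitment brings no gain.

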Our overall project consists of several parts. In Part 1 of the project, we have developed the MyREADY Transition™ BBD App intervention designed to improve transition readiness of youth prior to transfer of care. This current protocol is focused on Part 2, a mixed methods design featuring an RCT to test whether the MyREADY Transition™ BBD App intervention improves readiness for transition. Our RCT will use a pragmatic approach designed to test whether the intervention works under the usual conditions. The PRECIS-2 website⁷ (PRECIS – PRagmatic Explanatory Continuum Indicator Summary) is a tool for designing clinical trials on the pragmatic/explanatory continuum. The PRECIS-2 tool has nine domains: eligibility criteria, recruitment, setting, organization, flexibility-delivery, flexibility-adherence, follow-up, primary outcome, and primary analysis. All domains are scored from 1 (very explanatory) to 5 (very pragmatic). We will use the PRECIS-2 planning tool to facilitate discussion and consensus and to ultimately match design decisions with how the trial results are intended to be used. Integrated knowledge translation throughout the years of the project will draw on patient, parent/caregiver and health care stakeholder partnerships.

Outcome metrics are based on the Institute for Health care Improvement (IHI)'s Triple Aim framework⁸ (better health, better experience, at lower cost) with analysis stratified by region to account for local contextual factors. This comprehensive framework is poised for the creation of effective and efficient systems to optimize child and family outcomes.

CHILD-BRIGHT intentionally addresses a wide range of chronic diseases that share common functional limitations and health care needs. This non-categorical approach (i.e. including more than one medical condition or disability) enables interventions that can impact on larger populations of children above and beyond any diagnostic specific needs. The focus on BBD is strategically more integrative than diagnosis-specific research, thus promoting broader applicability.

STUDY AIMS AND HYPOTHESIS:

The MyREADY Transition™ BBD App intervention includes elements of transition planning to empower youth with BBD as they prepare for transfer into the adult health care system.

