We will request consent to obtain youth participant's Health Card Number to answer questions about use of health services like physician office visits, visits to emergency rooms and hospitalizations during

NOTE: CTO#1666 Amendment approved by HiREB on January 9, 2023. Target sample was 264 participants; however, we randomized 52 participants, and did not complete the full-scale RCT. Linking health card numbers with provincial administrative data is labour intensive and costly, and the small number would not provide meaningful results. As approved by ethics, we dropped the health economic outcome analysis (Health card number linking, Health Utilities Index (HUI), Resource Use Questionnaire (RUQ)) and destroy stored health card number data.

the study period (between the time a participant joins the study up until March 31, 2021). Participants have the option of participating in the study without sharing the youth's Health Card Number. The Health Card Number will allow us to link the information provided in the study with provincial data regarding the participant's use of health services. We will work with appropriate organizations in each province (Alberta, Ontario, Quebec, New Brunswick, and Nova Scotia) to gain approval to access provincial Health Services Administrative Data repositories. Health care services data recorded in the provincial administrative databases will be linked deterministically to the study data using the Health Card Number, partial date of birth and sex.

STATISTICAL ANALYSIS:

We will use regression analysis to adjust for baseline function as a sensitivity analysis to address any residual imbalance from the randomization.

The analysis and reporting of the internal pilot phase and main RCT results will follow CONSORT guidelines²³⁻²⁴. Patient demographics and baseline outcome variables (both primary and secondary) will be summarized using descriptive summary measures. All analyses will be performed using SAS 9.4 (Cary, NC). Analysis will be intention to treat. The table below provides a summary of study objectives, corresponding outcomes, hypotheses and methods of analyses. For subgroup analysis we will use interaction test (interaction of subgroup variable with the treatment or intervention variable).

Table 1: Study Objectives, Corresponding Outcomes, Hypotheses and Methods of Analyses

Objective	Outcome	Criterion for Success	Method of Analysis

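### The primary TRAQ analysis is specified in two incompatible ways (pooled t-test or region model with an interaction step), and baseline adjustment is left to a sensitivity analysis

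*Combined protocol and SAP*

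**What the plan says.** The protocol and SAP are one document, and the primary analysis is described in several places.

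- **STATISTICAL ANALYSIS, Table 1.** The primary outcome is "Change in TRAQ self-management score from Baseline to 6 months", with a t-test at p<0.05 as the method. No region term or baseline covariate is listed. The table is introduced thus: "The table below provides a summary of study objectives, corresponding outcomes, hypotheses and methods of analyses".
- **STATISTICAL ANALYSIS, opening sentence.** "We will use regression analysis to adjust for baseline function as a sensitivity analysis to address any residual imbalance from the randomization". Baseline function is not defined and need not mean baseline TRAQ.
- **SAMPLE.** "we will model the effect of region as a fixed effect rather than a random effect", which is meant to allow region-specific intervention effects. Then: "If no region by intervention interactions are found, the interaction terms will be dropped from the model", after which an overall effect is estimated.
- **SYNOPSIS.** Outcome metrics follow the Triple Aim framework, "with analysis stratified by region to account for local contextual factors".
- **Randomization.** Allocation is 1:1 and stratified by region.
- **Primary Measures, TRAQ.** Both arms complete the TRAQ at baseline and at 6 months.

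The amendment note says that 52 participants were randomized against a target of 264. It drops the health economic analysis and leaves the TRAQ analysis in place.

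**The concern.** A two-sample t-test on change has no region term and no interaction step, so it is not a short form of the model in the SAMPLE section. They are different analyses and will in general give different p-values. The plan does not say which is primary, what criterion decides that an interaction has been found, or which result is primary if one is. Under the SAMPLE wording, the form of the primary result also depends on a preliminary test on the same data.

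Separately, the plan collects the strongest obvious covariate (baseline TRAQ) and stratifies on region, yet Table 1 uses neither as a covariate. That is a loss of efficiency, not a bias. It matters more with 52 participants than with 264.

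**Working it through.** **1. The plan's own sample size.** Inputs from SAMPLE: difference 1 point, SD 1.02, α 0.05, power 90%. A two-sided, two-sample t-test (noncentral t) needs 23 per arm, with power 90.2%. Then 23 × 2 × 4 = 184. With 30% attrition, 23/0.7 rounds up to 33 per arm and region, and 33 × 8 = 264. The stated figures reproduce. They rest on a within-region comparison, that is, on the SAMPLE approach and not on Table 1's pooled test.

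**2. Variance with and without baseline adjustment.** Assumptions not in the documents: equal SDs (1.02) at both visits and correlation ρ between them of 0.3, 0.5 or 0.7.

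- Change score: SD = 1.02 × √(2(1−ρ)) = 1.207, 1.020, 0.790.
- ANCOVA residual: SD = 1.02 × √(1−ρ²) = 0.973, 0.883, 0.728.
- Variance ratio, ANCOVA to change score: (1−ρ²) / (2(1−ρ)) = (1+ρ)/2 = 0.65, 0.75, 0.85.

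The plan's use of a baseline SD of 1.02 for a change score matches ρ = 0.5.

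**3. Power.** Two-sided 5%, noncentral t. Degrees of freedom are 2n−2 for the t-test and 2n−6 for ANCOVA with baseline and four-level region. The 18 per arm comes from 52 × 0.7 = 36.4.

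| n per arm | Effect (points) | t-test, ρ 0.3/0.5/0.7 | ANCOVA, ρ 0.3/0.5/0.7 |
|---|---|---|---|
| 26 | 1 | 83/93/99% | 95/98/>99% |
| 18 | 1 | 67.5/81.5/95.8% | 84.7/90.8/97.8% |
| 26 | 0.5 (assumed) | 31/41/61% | 44/52/68% |

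At 26 per arm and ρ = 0.5, the standard error is 0.283 for the t-test and 0.245 for ANCOVA. The 95% CI half-widths are 0.57 and 0.49.

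At the planned 92 per arm, the t-test already has at least 98.7% power for 0.75 points or more, so little is lost there. For an assumed 0.5 points it has 80% against 93% for ANCOVA at ρ = 0.3, and 91% against 97% at ρ = 0.5.

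**4. Leaving region out.** Stratified allocation balances region across arms, so between-region variance inflates the t-test's standard error without adding to the true variability of the difference. In 20,000 simulated null trials per setting (4 regions, 6 per arm in each), with region explaining 0, 5, 10 or 20% of the variance in change (assumed), the true size of a nominal 5% t-test is about 4.9, 4.4, 3.9 and 2.8%. The region-adjusted test stays at 4.9–5.1%. The t-test is conservative, not invalid.

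**5. The interaction step.** Noncentral F with 3 and 8(n−1) degrees of freedom and λ = (n/2) × Σ(δ − mean δ)²/SD². Assumptions: SD of change 1.02, equal numbers per region and arm, no attrition. Regional counts are not given, so n = 52/8 = 6.5 per cell is itself an assumption.

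- Regional effects (1, 1, 1, 0): Σ = 0.75, λ = 3.25 × 0.75/1.0404 = 2.34, power 20%.
- Regional effects (1, 1, 0, 0): Σ = 1, λ = 3.25/1.0404 = 3.12, power 26%.

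With the SD of change implied by ρ = 0.3 the two figures are 16% and 20%; with ρ = 0.7 they are 32% and 42%. At the planned 23 per cell and SD 1.02 they are 66% and 80%. Failing to find an interaction is therefore weak evidence that there is none, most of all at the size reached.

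**The case against.** The best counter-argument has four parts.

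- **The t-test is legitimate.** It is valid, it already uses baseline TRAQ through the change score, and a baseline-adjusted analysis is planned. At ρ = 0.5, which the plan's SD implies, ANCOVA moves power only from 93% to 98% at 26 per arm for the planned effect. This is correct, and the gain shrinks as ρ approaches 1. The adjustment point is about precision and does not show that the t-test is wrong.
- **The SYNOPSIS clause may not cover TRAQ.** It refers to Triple Aim metrics, whose matching headings fall under Secondary Measures. That reading is fair. The contradiction does not need the clause, because SAMPLE and Table 1 conflict without it.
- **An interaction test is named.** STATISTICAL ANALYSIS mentions interaction tests for subgroups, and α is 0.05 elsewhere. That hints at a criterion but is not applied to the region step.
- **The trial stopped at 52.** A confirmatory test may carry less weight now. But the amendment removes only the health economic analysis, the TRAQ test remains, and the choice of analysis matters more in a small sample.

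Naming either existing analysis would also remove the contradiction. The case for ANCOVA is that it removes the contradiction and gains precision from data already held.

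**Conclusion.** The concern holds. The plan gives two different primary analyses and no rule for choosing between them; this is the main defect and depends on no assumption.

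The efficiency point is secondary. Under equal variances and ρ between 0.3 and 0.7, the unadjusted t-test gives up 15–35% of the variance that baseline adjustment would remove. That is worth up to about 12 percentage points of power at 26 per arm and 17 at 18 per arm for the planned 1-point effect. At the planned 92 per arm the loss is negligible for effects of 0.75 points or more, but not for 0.5 points at low ρ. Omitting region makes the t-test somewhat conservative if region predicts change. The interaction step is too weak at 52 participants to choose the primary model under any of the settings examined.

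**What to change.** 1. Name one primary analysis: ANCOVA of 6-month TRAQ self-management on arm, baseline TRAQ self-management and region (four-level fixed effect), reporting the adjusted difference with its 95% CI. Using change as the dependent variable with the same covariates gives the same arm coefficient, so the stated outcome need not be altered.
2. Use the same form for TRAQ self-advocacy.
3. Keep the unadjusted change-score t-test as a sensitivity analysis.
4. Report the region-by-intervention interaction as a separate secondary test that does not determine the primary model.
5. Align SYNOPSIS, SAMPLE, the text of STATISTICAL ANALYSIS and Table 1.
6. Record, with a date, that the choice was made before unblinded outcome data were examined. If they have already been examined, say so and report both analyses.

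The cost is wording in four places and a dated record; the Randomization section already plans blinded data analysis. Baseline TRAQ and region are already collected. The model uses four more degrees of freedom than the t-test (one for baseline, three for region), which the power figures above already allow for.
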